PROTOCOL

Full Study Title : A Prospective, Controlled, Randomised, Double Blind, Single Centre Study, Comparing the Effectiveness of Physiotherapy and Image Guided Injection of the Lateral Epicondyle of the Common Extensor Tendon with either Sodium Hyaluronate with Mannitol (Ostenil Tendon[™]), Platelet Rich Plasma (PRP), or Sham Injection on Pain and Function in Patients with Lateral Epicondyle Tendinosis.

Modified title compliant with character restrictions on clinicaltrials.gov register:

A Prospective, Double Blind, Single Centre, RCT, Comparing the Effectiveness of Physiotherapy in addition to one of 3 types of Image Guided Injection of the Common Extensor Tendon, on Pain and Function in Patients with Tennis Elbow.

Version 10 23rd May 2018

Brief Title: Comparing Injection Treatments for Tennis Elbow (CITTE) Trial.

IRAS number 223134

Investigators: [name]

Study venue: Wrightington Hospital

Aim : To determine the effect of a structure physiotherapy programme and a single image guided peri-tendinous injection to the lateral epicondyle, of either; Sodium Hyaluronate with mannitol (Ostenil Tendon[™]), Platelet Rich Plasma (PRP), or sham Injection on pain and function in patients with established elbow tendinopathy.

Background.

Tendinopathy of the common extensor tendon is one of the most prevalent musculoskeletal disorders of the arm, typically attributed to excessive use of the extensor and/or flexor muscles of the wrist, it is an overloading-induced injury resulting in pain and functional disability, often leading to limitation or cessation of activity and absence from work. Historically this syndrome has been referred to as lateral epicondylitis, which presents somewhat of a misnomer as histological evaluation typically displays no evidence of either acute or chronic inflammation.^[1,2] Rather, repetitive muscle contraction leads to a neurocellular response provoking degradation by enzymes leading to angiofibroblastic degeneration and collagen disarray. Thus the current nomenclature includes 'lateral epicondyle tendinopathy', 'lateral epicondyle tendinosis', 'lateral epicondylalgia' or, more colloquially, 'tennis elbow'.^[2]

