Krogh *et al.* examined whether a single injection of platelet-rich plasma (PRP) is more effective than saline or glucocorticoid in reducing pain in adults with lateral epicondyle tendinopathy at three months post-injection.^[47] The authors conclude that neither injection of PRP nor glucocorticoid was superior to saline with regard to pain reduction in lateral epicondyle tendinopathy at the primary end point (3 months), however the study may be criticized due to the needling technique used to administer the saline, as this may have a therapeutic effect.

The current study will seek to identify any statistically significant differences in pain and function, as evinced by validated objective and subjective measures, in patients with a diagnosis of Lateral Epicondyle Tendinopathy/Entheseopathy, following a single, peri-tendinous injection into the affected elbow, administered under real time ultra-sonographic imaging, of either; 2ml 2% solution of Non-Animal Derived, Non-Chemically Modified Sodium Hyaluronate with Mannitol (Ostenil Tendon), or 2ml of PRP prepared with the Biomet Recover Miniplatelet System, reported to provide 8x the circulating concentration of platelets, or a subcutaneous sham injection under ultrasound control. All patients will undergo a standardised physiotherapy programme post injection.

Methodology.

Study Design. Prospective, randomised, controlled, double blinded, single centre trial.

Selection Criteria. Invitations to participate in the study will be extended to male and female patients, 18 years and above, referred to the Orthopaedic Departments who receive a diagnosis of Lateral Condyle Tendinosis (with or without degenerative changes) with symptoms present for > 3 months, whose symptoms and clinical evaluation warrant the prescription of a peritendinous injection to relieve symptoms and who are competent to give informed consent.

Demographic data collection Age Handedness Occupation Ethnicity

Exclusion Criteria.

- Absence of tenderness at the lateral epicondyle.
- Congenital or traumatic bio-mechanical deformities of Elbow complex.
- Previous Corticosteroidal, Local Anaesthetic, PRP or Hyaluronic Acid injections to target elbow within the last three months.
- Known hypersensitivity to PRP, Hyaluronic acid or any excipients associated with any of the prescribed injections.
- Known contra-indication to any treatments constituting normal/appropriate therapy in the view of the Consulting clinician.

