Consenting participants will be randomised to Study Group A (physio and PRP), Study Group B (physio and Ostenil Tendon[™]), or Control Group C (physio and sham injection) once informed consent has been recorded and baseline data has been collected.

Treatment and follow-up will be the same for those patients who wish to take part in the study and for those patients who decline to take part but whose condition makes a peri-tendinous injection clinically appropriate. Following informed consent, patients will be assessed for demographic detail (age, gender, ethnicity, occupation, affected elbow, height and weight/BMI, duration of symptoms, relevant diagnosis, current medication), and given patient completed questionnaires to assess pain and function (Oxford Elbow Score (OES), Quick DASH Score, 100 mm visual analogue pain scale with terminal descriptors), Hospital Anxiety and Depression (HAD) Score and asked to complete EQ5D at the initial consultation (V1).

Treatment: Consenting patients will attend for the injection to be administered under ultrasound guidance. All participants will have 30ml of whole venous blood withdrawn under aseptic conditions.

Out of sight of the patient the whole venous blood will either be;

placed in the cell separator and centrifuged at 32000 rpm for 15 minutes for subjects in group A. During the centrifugation process 2ml of 2% plain lidocaine will be injected into the subcutaneous layer at the site of injection of the PRP. One millilitre (2ml) of PRP produced will be drawn into a syringe wrapped in silver foil and injected under ultrasound control via a blue (20 gauge) hypodermic needle into the lateral epicondyle using a peppering technique.

Or

discarded for those in group B and C. The centrifuge will be set to run at 32000rpm for 15 minutes with a saline counterbalance. During the centrifugation process 2ml of 2% plain lidocaine will be injected into the subcutaneous layer at the site of injection. For those in group B a pre-prepared "Ostenil Tendon" syringe will be wrapped in silver foil and 2ml will be injected into the peri-tendinous area via a blue (20 gauge) hypodermic needle under ultrasound control.

For those in group C an empty syringe wrapped in silver foil with a blue (20 gauge) hypodermic needle will be used to perform a sham injection into the subcutaneous tissue only by passing the needle into the tissue with no injectate.

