During the procedure the patient will be distracted by being asked to confirm their personal details.

Patients will be given pain report diaries which will be completed on days 1, 2, 3, 7, and 14, and at 6 weeks, 12 weeks (final clinical follow up visit prior to discharge).-Patients will be taught home exercises by a blinded physiotherapist prior to discharge, a formal class based physiotherapy programme will commence at 5-15 days post injection. The patient will be assessed by a blinded clinician at 3 months and 12 months post treatment. Telephone follow-up calls will be made to patients 3 months and 12 months post treatment if the patient declines to attend a follow-up appointment. The Consulting physician will discharge patients from his direct care at 12 weeks unless enduring or subsequently manifesting symptoms persist. Pain scores, amount of rescue medication (codeine & Paracetamol) and QOL questionnaires will be completed at all visits. The OES, qDASH, HAD and EQ5D will be completed at 3 and 12 month reviews.

Patients who successfully complete both 3 month and 12 months outcome questionnaires with be entered into a raffle to win an iPad tablet computer.

Primary Measure of Outcome.

The difference in Objective Functional Assessment as evinced by Quick DASH, at 12 months

Secondary Measures of Outcome.

The difference in Objective Pain and Functional Assessment as evinced by OES and 100 point VAS with terminal descriptors at 12 months

Change in EQ5D General Health Questionnaire.

Relationship of pre-injection HAD score to outcome.

Change in HAD score at 12months

Use of Rescue Medication.

Number of Patients.

The proposed randomized controlled double blind (single centre) trial design will have 80% power (1- β) to reject the null hypothesis, with an α (type I error, i.e. level of statistical significance) set at 0.05. Assuming a clinically significant [mean] difference (δ) of 15 Q-DASH score units between groups together with an estimated sample standard deviation (σ) of 22.5 (Biomet study – based on Q-DASH score for PRP arm) which gives an 'n' for each trial arm (assuming equal group sizes) of at least 35 analyzable patients in each of the three groups (A,B &C) and given a possible attrition rate of about 16% the CITTE trial will probably therefore need a total sample size of at least 123 of patients, approximately.

Statistical Analysis.

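### The 35 per arm matches one unadjusted two-group test, but the three-arm plan names no primary contrast, test order or multiplicity rule for 12-month Quick DASH

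*Combined protocol and SAP*

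**What the plan says.** All references are to the combined protocol and SAP.

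- **Primary Measure of Outcome**: "The difference in Objective Functional Assessment as evinced by Quick DASH, at 12 months". Neither the groups nor the contrast is named.
- **Number of Patients**: "80% power (1- β) to reject the null hypothesis, with an α (type I error, i.e. level of statistical significance) set at 0.05". The effect is given as "Assuming a clinically significant [mean] difference (δ) of 15 Q-DASH score units between groups", with SD 22.5 taken from the PRP arm of an earlier study. The result is at least 35 analysable patients in each of three equal groups, and about 123 in total allowing for roughly 16% attrition. Sidedness is not stated.
- **Statistical Analysis**: Quick DASH is grouped with VAS, OES, EQ5D and other scores. These are to be compared by t test or by Mann-Whitney/Wilcoxon. ANOVA is only a possibility, and is mentioned for correlations. Kruskal-Wallis and Jonckheere appear in brackets on the rank route. No test is fixed for the 12-month comparison, and there is no order of tests or multiplicity rule.
- **Elsewhere**: the modified title reads "Comparing the Effectiveness of Physiotherapy in addition to one of 3 types of Image Guided Injection of the Common Extensor Tendon". The study objective, at the end of the Background, reads "The current study will seek to identify any statistically significant differences in pain and function". The randomisation text in Procedure gives a control label to one arm only: "or Control Group C (physio and sham injection) once informed consent has been recorded".
- **Baseline data**: Procedure has participants complete "patient completed questionnaires to assess pain and function (Oxford Elbow Score (OES), Quick DASH Score" after consent and before the injection.

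**The concern.** Three arms give three pairwise comparisons, or two if only those against sham matter. One null hypothesis, one alpha and one power are enough for a single contrast or a single overall test, but the plan commits to neither. Two things follow.

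First, the listed two-group tests, applied to several pairs at 0.05 each, do not hold 5% across the primary outcome. If the error is held at 5% over those comparisons, the planned size does not give 80% for a particular pair.

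Second, which contrast and which test are reported as primary could be settled after the data are seen.

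**Working it through.** **Inputs.** From Number of Patients: difference 15, SD 22.5, alpha 0.05, power 80%, 35 analysable per arm, three equal arms. Assumed: two-sided tests (one-sided gives 28 per arm, which does not match the plan), normal data, SD 22.5 in every arm and, until step 5, no baseline adjustment.

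**1. Reproduce the plan's figure.** Two-group formula: n = 2(1.960 + 0.842)² × 22.5² / 15² = 35.3 per arm. At 35 per arm, power is 79.6% by the normal approximation and 78.5% by noncentral t. The stated 35 is therefore one unadjusted pairwise calculation, to rounding.

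**2. Does 35 also fit an overall test?** For a one-way F test, f = SD of the three means / 22.5, with noncentrality 105 × f².

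| Means | f | Noncentrality | Power at 35 per arm | n per arm for 80% |
|---|---|---|---|---|
| 0 / 0 / 15 | 0.314 | 10.37 | 82% | 34 |
| 0 / 7.5 / 15 | 0.272 | 7.78 | 69% | 45 |

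The figure fits an overall test under one pattern of means but not the other, so it points to the pairwise formula without excluding the F test.

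**3. False positives if pairs are tested unadjusted** (simulation, no true differences, 35 per arm, each test at 0.05):
- at least one of two tests against sham: about 9.1%
- at least one of all three pairs: about 12.2%

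The independence bounds are 1 − 0.95² = 9.75% and 1 − 0.95³ = 14.3%. The simulated rates are lower because the pairs share arms. Mann-Whitney tests give the same figures to within 0.1 percentage point.

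**4. Power for a given 15-unit pair if error is held at 5%** (35 per arm):

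| Rule | Power |
|---|---|
| Bonferroni, three pairs (0.0167 each) | 63% |
| Bonferroni, two against sham (0.025 each) | 69% |
| F test at 0.05, then t at 0.05 | 68% (0/7.5/15) to 74% (0/0/15) |
| One named contrast at 0.05, t test | 78.5% |

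Under the gate, at least one pair is significant with about 82% probability if one arm differs by 15 from two equal arms, and 69% for means 0/7.5/15. The gate holds the error: simulated error is 5.0% with no differences, and 4.9% on the equal pair when the third arm differs by 15. On the rank route with the same normal data, a single Mann-Whitney test has 76% power, and Kruskal-Wallis followed by Mann-Whitney 65–71%.

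**5. Baseline adjustment.** Adjusting for baseline replaces the SD by 22.5 × √(1 − r²), which is 21.5 at r = 0.3 and 19.5 at r = 0.5. The documents give no r, so these values are illustrative. They use 34 per arm, a slightly cautious figure: 123/3 = 41, and 41 × 0.84 = 34.4. Gated power for a 15-unit pair is 71–77% at r = 0.3 and 80–85% at r = 0.5. For one named contrast it is 81% and 88%.

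**The case against.** Four points can be made for the plan.

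- **The sample size has an obvious basis.** One difference, one SD and one n per arm are the inputs to the two-group formula, and the result matches. This stands. A reader might infer that alpha and power correspond to no test at all, or that 35 is miscalculated; neither is supported. What is missing is which pair or pairs the calculation covers.
- **The analysis section does link its tests to Quick DASH.** This also stands: Quick DASH is among the scores to which the tests apply, and Kruskal-Wallis is a three-group test. But it is an option in brackets, not a required step ahead of the pairs.
- **The title, objective and arm labels are compatible.** They are. A reader might see a contradiction between comparing three injections, seeking any difference and naming one control. An ordinary three-arm trial can do all three. These texts simply do not choose a primary contrast.
- **Two different products may each be compared with sham as separate questions at 0.05.** This is a defensible convention, and under it the 9% and 12% are not errors. The plan does not adopt it, however, and adopting it would still leave the primary contrast and test unnamed.

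Power also looks better on some criteria. If both active arms differ from sham by 15, at least one unadjusted contrast with sham succeeds about 90% of the time, although both succeed only about 67% of the time.

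**Conclusion.** The concern holds in a limited form, and it should be fixed. The planned size supports one two-sided pairwise contrast at close to 80% power, but the plan does not say which contrast, or how the other pairs are to be handled.

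It would go too far to say that the trial's error rate is inflated. The excess to about 9% or 12% follows only if two-group tests are run unadjusted on two or three pairs and 0.05 is meant for the primary outcome as a whole. If 5% is held across the comparisons, power for a given 15-unit pair is about 63–74%.

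All power figures assume SD 22.5 in every arm, although the plan takes it from a PRP arm alone. They also assume normal data, two-sided tests and 35 analysable per arm, with no baseline adjustment.

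**What to change.** In Number of Patients and Statistical Analysis, state one rule for 12-month Quick DASH, either:

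- **(a)** require an overall three-arm test at two-sided 0.05, and test pairs at 0.05 only if it is significant (with three arms this holds the error at 5%); or
- **(b)** name one primary contrast at two-sided 0.05, with the others tested in a fixed sequence after it.

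Fix the test (t/ANOVA or rank) in advance and restate power for the rule chosen. At 35 per arm on the t/ANOVA route this is 68–74% for a given pair under (a), or 78.5% for the named contrast under (b). Merely declaring 0.05 per comparison would document the choice without controlling the overall error; if that is the intention, the 9% or 12% should be stated beside it.

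Under either rule, adjust the 12-month score for baseline Quick DASH, and show the power gain over a range of correlations.

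**Cost.** A few sentences, and no extra patients or data if the restated power is accepted. Under (a) the stated power is less favourable, and whether adjustment restores 80% depends on a correlation that the documents do not give. Under (b) the remaining contrasts lose primary status and depend on the first. Keeping 80% for every pair by Bonferroni instead would need 43 per arm (two tests) or 48 (three) by the normal formula. That is 129/0.84 ≈ 154 or 144/0.84 ≈ 172 randomised, against 123 planned.

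### The stated minimum of about 123 patients is not expected to leave the stated 35 analysable patients per arm at the stated 16% attrition; the consistent figure is 125, or 126 in equal arms

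*Combined protocol and SAP*

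**What the plan says.** All the sizing figures are in the Number of Patients section of the protocol. It says the "trial design will have 80% power", with alpha ("type I error, i.e. level of statistical significance) set at 0.05"). The target is a difference "of 15 Q-DASH score units between groups together with an estimated sample standard deviation" of 22.5, taken from the PRP arm of an earlier study. From these it derives "at least 35 analyzable patients in each of the three groups", with equal groups assumed. It then allows for drop-out: "possible attrition rate of about 16% the CITTE trial will probably therefore need a total sample size of at least 123 of patients, approximately".

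The section does not say whether the test is one- or two-sided, which test or formula was used, whether the power refers to one pair of arms or to all three together, or how the attrition allowance was applied. The Statistical Analysis section does not settle this. It lists t tests, a possible ANOVA (mentioned there for correlations) and rank-based alternatives for two or more groups.

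**The concern.** The total is presented as following from the per-arm floor and the attrition rate, so a reader should be able to get from 35 and 16% to 123. Dividing by the retained proportion gives 125. The stated minimum total is therefore not expected to yield the stated minimum per arm under the protocol's own assumption.

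A second, weaker point concerns the 35 itself. Under the most natural reading of the inputs the requirement is slightly above 35, so 80% power is not quite reached even if the floor is met.

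What is at stake is the accuracy of the trial's only justification of its size, which should support the 12-month Quick DASH comparison. The amount is small.

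**Working it through.** **Inputs, all from Number of Patients:** difference 15; SD 22.5; alpha 0.05; power 80%; three equal arms; floor of 35 per arm, so 3 × 35 = 105 in total; attrition 16%; total 123. Sidedness and test are not given.

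**1. Reproducing the 35.** For two means, n per arm = 2 × (z_alpha + z_power)² × (SD/difference)², with SD/difference = 22.5/15 = 1.5.
- Two-sided: 2 × (1.960 + 0.8416)² × 2.25 = 35.32. Rounded up, this is 36.
- One-sided: 2 × (1.645 + 0.8416)² × 2.25 = 27.82, or 28.

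Only the two-sided version comes near 35, so it is assumed below. It reproduces the stated figure to within one patient.

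**2. Reproducing the 123.** Multiplying by 1.16 gives it: 35 × 1.16 = 40.6, rounded up to 41, and 3 × 41 = 123. Division with a loss of 14.6% also gives it: 105/0.854 = 123. The protocol does not state its route, so neither can be attributed to it.

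**3. The total needed at 16% loss.** This step needs no assumption about test or sidedness. Required total = 105/(1 − 0.16) = 105/0.84 = 125. With equal whole arms, 35/0.84 = 41.7, so 42 per arm and 126.

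**4. What 123 delivers.** 123 × 0.84 = 103.3, or 34.4 per arm, which is 1.7 patients below 105. The break-even loss is 1 − 105/123 = 14.6%. Expected analysable patients from 123:

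| Loss | Expected analysable |
|---|---|
| 14.5% | 105.2 |
| 15% | 104.6 |
| 15.5% | 103.9 |
| 16% | 103.3 |
| 16.5% | 102.7 |

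**5. Set against chance.** If patients are lost independently with probability 0.16, the SD of the number retained from 123 is √(123 × 0.84 × 0.16) = 4.1. The chance of retaining at least 105 in total is 40% at 123, 56% at 125 and 64% at 126.

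**6. Power, conditional on one unadjusted two-sided pairwise comparison:**

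| Analysable per arm | Normal approximation | t test |
|---|---|---|
| 34 | 78.5% | 77.3% |
| 34.4 (123 at 16% loss) | 79.0% | 77.8% |
| 35 (the floor) | 79.6% | 78.5% |
| 35.3 (126 at 16% loss) | 80.0% | 78.8% |
| 36 | 80.7% | 79.7% |

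At 34 to 34.4 per arm the shortfall from 80% is 1.0 to 2.7 points.

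**7. If 36 per arm is used.** 36/0.84 = 42.9, so 43 per arm and 129 in total.

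**The case against.** The strongest reply is that the passage is openly approximate. The attrition rate is only possible and rounded, and the total is qualified both as a minimum and as approximate. Loss 1.4 points lower than 16% would make 123 sufficient. Because the minimum is open-ended, randomising 125 or 126 would breach nothing. The protocol also includes steps that may limit loss, such as telephone follow-up and an incentive for completing both questionnaires. The gap of 1.7 patients is well inside the drop-out SD of 4.1.

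Most of this stands, and it fixes the size of the point. It does not make 123 the right minimum. A minimum derived from a floor and a loss rate should be expected to meet that floor at that rate, and chance variation does not justify centring the expectation below it.

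The reply on the per-arm figure also has force. The section speaks of rejecting the null hypothesis in a three-group trial and names no test. With a three-group F test and one arm differing from the other two by 15, power is 81.8% at 35 per arm and 81.1% at 34.4, so both stated figures would meet 80%. If the third arm lies midway, power at 35 is only 69%. The protocol specifies neither pattern, and the pairwise formula is the closest match to 35. The power shortfall must therefore stay conditional on that reading.

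A reader might infer three stronger things, none of which the documents support:
- **That the section contradicts itself.** It does not, since a total of 126 would satisfy every statement in it.
- **That 35 is a plain rounding error for 36.** That holds only for the pairwise two-sided formula, which is not stated.
- **That the sponsor multiplied where it should have divided.** The arithmetic matches, but no route is given.

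**Conclusion.** The point holds in a minor form. On the protocol's own figures, with no assumption about the test, 123 is two patients below the 125 needed to expect 105 analysable patients at 16% loss, and three below the 126 needed in equal arms. It is expected to leave about 103 patients, or 34.4 per arm.

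Conditional on one unadjusted two-sided pairwise comparison, 35 per arm is itself just under 80% power, and the number expected from 123 gives about 79% (normal approximation) or 78% (t test). This does not show that the design fails or is materially underpowered. It shows that the stated figures are slightly more favourable than their inputs allow.

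**What to change.** Keep 123, name the test and sidedness used for sizing, and restate the figures in one sentence. If the pairwise reading is the intended one, it could run: *With 123 patients randomised and about 16% attrition, about 103 (34 per arm) are expected to be analysable, giving about 78% to 79% power for a single unadjusted two-sided pairwise comparison, for a difference of 15 with SD 22.5.* Once the test is named, the range can be cut to one value: 79% by the normal approximation or 78% by the t test.

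There are two alternatives if a floor is to be kept:
- **35 per arm:** state the minimum total as 126. This repairs the attrition step only.
- **36 per arm,** so that power by the normal approximation reaches 80%: state 129. The t test at 36 per arm still gives 79.7%.

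The preferred change costs one sentence and a stated power 1 to 3 points lower, with no extra patients. The alternatives add three or six patients to the stated minimum. None of them changes the analysis.

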All quantitative data - age, gender, duration of symptoms, disease progression, target joint, Height, weight and BMI, will be analysed using the most appropriate non-parametric tests. VAS, qDASH and OES score Inventories, EQ5D, Blinded Assessor and escape medication scores will be tested for homogeneity of variance (Chi sq/F test), mean scores calculated, and then either *t* tested (with possible ANOVA for correlations between pain, function, strength etc) or Mann-Whitney/ Wilcoxon rank sum (Kruskall Wallis differences /Jonkheere trend).

Interventions

Physiotherapy protocol

After the injection and prior to discharge a physiotherapist will teach patients eccentric loading exercises of the wrist extensors. They will be instructed to commence the exercises at day 1 post injection. They will be advised to carry out 3 sets of 15 repetitions, 3 times per day. An accompanying exercise sheet will advise to increase the load as symptoms permit. It will be suggested to commence with a half filled 500ml bottle of water. In addition a simple common extensor stretch will be taught to use following the eccentric exercises.

At 5-15 days post injection the patients will commence an out-patient class based physiotherapy programme. The class will be held 2 weekly by a blinded physiotherapist. After being taught the exercises on an 1:1 basis, the patients will be supervised during a circuit style exercise programme. The exercise programme will include eccentric loading of the common extensors, and upper limb strengthening involving the full kinetic chain, in particular the rotator cuff and scapular muscles. Each patient will be supervised and monitored to improve technique, and to increase the load. Patients will be provided with a home exercise programme which will reflect the class exercises.

Study GROUP A Product Dose, Presentation, and Mode of Administration.

2ml unbuffered PRP prepared with **Zimmer/Biomet Recover Mini-platelet** system administered via intratendinous injection under ultrasound.

Study GROUP B Product Dose, Presentation, and Mode of Administration.

Ostenil[™] Tendon (40mg/2ml of bio-fermentation source Sodium Hyaluronate with 10mg Mannitol in a pre-filled syringe). To be administered via peritendinous injection under ultrasound.

Licensed indication in the EU: For the treatment of pain and restricted mobility in tendon disorders.

Active Ingredient; Sodium Hyaluronate / Mannitol

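### Baseline QuickDASH is collected before randomisation, but the analysis of 12-month QuickDASH names no adjustment for it

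*Combined protocol and SAP*

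**What the plan says.** The Procedure section has patients "given patient completed questionnaires to assess pain and function (Oxford Elbow Score (OES), Quick DASH Score" and other instruments at the initial consultation (V1). Randomisation follows "once informed consent has been recorded and baseline data has been collected". Baseline QuickDASH is therefore a pre-randomisation measurement that the trial already plans to hold for every participant.

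The primary outcome is "The difference in Objective Functional Assessment as evinced by Quick DASH, at 12 months". The Number of Patients section assumes a difference "of 15 Q-DASH score units between groups together with an estimated sample standard deviation" of 22.5, taken from the QuickDASH score in the PRP arm of another study.

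Statistical Analysis is the only analysis text. It states that "VAS, qDASH and OES score Inventories, EQ5D, Blinded Assessor and escape medication scores will be tested for homogeneity of variance". The scores are then either t "tested (with possible ANOVA for correlations between pain, function, strength etc") or compared by "Mann-Whitney/ Wilcoxon rank sum (Kruskall Wallis differences /Jonkheere trend"). No covariate, regression, ANCOVA or mixed model appears. Among the secondary outcomes, the one baseline score listed as a predictor of outcome is HAD: "Relationship of pre-injection HAD score to outcome". Change from baseline is named for EQ5D and HAD, but not for QuickDASH.

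**The concern.** When a baseline measure of the outcome is available and correlates with the final score, leaving it out of the analysis discards information already paid for. The residual variance, and so the confidence interval, is wider than it need be. The design has little slack, since its planned power is at or just below 80%.

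The text also leaves open whether QuickDASH is analysed as the raw 12-month score or as change from baseline. The wording leans to the raw score, because change is reserved for EQ5D and HAD, but it does not say so. The two analyses can differ a good deal in power. A baseline-adjusted model makes the choice irrelevant: with baseline as covariate, raw score and change score give the same treatment effect.

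**Working it through.** **Inputs from Number of Patients:** 35 analysable per arm, difference 15, SD 22.5, alpha 0.05, power 80%.

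**Assumptions:** two-sided test; 22.5 is the raw 12-month SD; one pairwise contrast without multiplicity adjustment; correlation r between baseline and 12-month QuickDASH varied from 0 to 0.6, because the documents give none.

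**1. The plan's own figure.** By the normal formula, n = 2 × [22.5 × (1.96 + 0.842) / 15]² = 35.3 per arm, which rounds up to 36 against the stated 35. Power at 35 per arm is 79.6% by the normal formula and 78.5% by the exact t test (68 df). For the total, 35 × 1.16 = 40.6, so 41 per arm, and 41 × 3 = 123. The stated size reproduces closely and is not in dispute.

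**2. Unadjusted analysis.** The standard error is 22.5 × √(2/35) = 5.38. Power is 78.5% with two arms, or 78.9% when the variance is pooled over three arms (102 df). The mean 95% CI half-width is 10.7 or 10.6 units.

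**3. Adjusted analysis.** The residual SD is 22.5 × √(1 − r²). The contrast variance is residual variance × (2/35) × (1 + F/m), with F ~ F(1, m) and m = 34 × number of arms. The last factor allows for chance baseline imbalance. One degree of freedom is lost, and noncentral-t power is averaged over F.

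| r | Residual SD | Power, two arms | Power, three arms | Mean CI half-width, three arms |
|---|---|---|---|---|
| unadjusted | 22.5 | 78.5% | 78.9% | 10.6 |
| 0 | 22.5 | 77.9% | 78.5% | 10.7 |
| 0.1 | 22.4 | 78.3% | 78.9% | 10.6 |
| 0.2 | 22.0 | 79.5% | 80.1% | 10.5 |
| 0.3 | 21.5 | 81.6% | 82.2% | 10.2 |
| 0.5 | 19.5 | 88.3% | 88.8% | 9.3 |
| 0.6 | 18.0 | 92.6% | 93.0% | 8.6 |

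The half-widths are from simulation. Simulating 400,000 trials per cell agreed with each power figure to about 0.1 points.

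**4. If 22.5 is instead a change-score SD** (equal SDs at both times), the raw SD is 22.5 / √(2(1 − r)). Three-arm power is then:

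| r | Raw SD | Raw-score test | Change-score test | Adjusted model |
|---|---|---|---|---|
| 0.2 | 17.8 | 94% | 79% | 94% |
| 0.3 | 19.0 | 90% | 79% | 93% |
| 0.5 | 22.5 | 79% | 79% | 89% |
| 0.6 | 25.2 | 70% | 79% | 87% |

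The adjusted model is at least as good as either alternative in each of these cells.

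**5. A change-score t test is not a substitute.** If 22.5 is a raw SD, the change SD is 22.5 × √(2(1 − r)). At r = 0.3 that is 26.6, and three-arm power is about 65%, against 82% adjusted. At r = 0.5 it is 22.5, so power is 79% against 89%.

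**The case against.** The strongest reply is that nothing here is invalid. A t test or rank test of a randomised 12-month score is unbiased and the stated sample size stands, so preferring adjustment is advice on efficiency. That is accepted, and the point claims no more.

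The second reply is that the gain depends on a correlation the documents do not supply, and what they do say may point to a low one. Treatment Options reports that over 80% of patients improve within a year, the Exclusion Criteria remove pain scores below 4/10, and the outcome comes 12 months later. Widespread recovery and a narrowed baseline range could both weaken the correlation. This also stands. At 0.2 to 0.3 the three-arm gain is 1 to 3 points of power, and the figures near 90% need 0.5 or more, for which the documents give no support. The trade still favours adjustment, because the worst case costs 0.4 to 0.6 points.

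Third, if change from baseline is what will be tested, baseline is already in use. The text does not say this for QuickDASH, and in every case worked above a change-score test does worse than the adjusted model. The change outcomes for EQ5D and HAD use their own baselines and do nothing for the primary comparison.

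**Conclusion.** The concern holds as a missed gain in precision. The plan collects baseline QuickDASH before randomisation and does not say that it will use it in the primary comparison. For one contrast in a three-arm model, adjustment raises power from 78.9% to 80.1% at a correlation of 0.2, 82.2% at 0.3 and 88.8% at 0.5. The mean CI half-width falls from 10.6 to 10.5, 10.2 and 9.3 units. The gain disappears at about 0.1.

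These figures rest on an assumed correlation, a two-sided test and 22.5 being the raw 12-month SD. If 22.5 is a change-score SD, the levels differ but adjustment is still at least as good at each correlation tried from 0.2 to 0.6. The change should be made, but the plan is not unsound without it.

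**What to change.** In Statistical Analysis, name as the primary analysis a linear model of 12-month QuickDASH on arm with baseline QuickDASH as covariate, fitted to all three arms. Report adjusted mean differences with 95% CIs, using robust standard errors if the variances differ, and keep one rank test as a sensitivity analysis.

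Three small additions belong in the same edit:
- State in advance which pairwise contrasts are primary, for example A versus C and B versus C.
- Use the same model for OES, VAS, EQ5D and HAD where a linear model suits them.
- Either give the arm order for the Jonckheere trend test or drop it.

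The cost is wording only, with no new data, visits or patients. If baseline and 12-month scores proved uncorrelated, the loss would be about 0.4 points of power in the three-arm model, or 0.6 in a two-arm model. The planned total of 123 need not change.
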